Can *Lactobacillus acidophilus* decrease the risk of postmenopausal osteoporosis in women?

Short Description

Background

The current recommendations for treating bone diseases are estrogen therapy and pharmacological agents. However, those treatments increase the risk of cancers and are not prescribed for long-term use. *Lactobacillus acidophilus* in ovariectomized mice could inhibit osteoclastogenic cells and promote anti-osteoclastogenic cells.

Aim of study

This study aims to evaluate the effect of *L. acidophilus* supplementation on calcium status and bone densitometry in postmenopausal women in a randomized, double-blind placebo-controlled study.

Study design

This study has three steps; namely, **1st step** is to prepare the diet supplementation of probiotics (*L. acidophilus* 1×10^9 CFU). **2nd step** is to perform the randomized, double-blind placebo-controlled clinical trial. **3rd step** is to analyze the effects of *L. acidophilus* in postmenopausal women.

Methods & Analysis

60 women of postmenopausal osteoporosis will be recruited by following inclusion and exclusion criteria. Participants will be randomized and divided into two groups to take a capsule containing probiotics and a placebo for 12 weeks. Before and after the intervention, several parameters will be conducted, such as the bone turnover and hormones parameter in blood using ELISA, the calcium mineralization in hair sample using AAS, the bone densitometry analysis in bone using DXA.

Research Design

Study settings

This study will be conducted within two (2) years for research activity and one (1) year for the publication period. There are three steps within this study; namely, **1st step** is to prepare the sample of *L. acidophilus* as diet supplementation. Probiotic capsules will contain *L. acidophilus* 1×10^9 CFU. **2nd step** is to perform the randomized, double-blind placebo-controlled clinical trial of *L. acidophilus* supplementation for twelve weeks (Figure 1). **3rd step** is to analyze the effects of *L. acidophilus* in postmenopausal women.

[figure not shown]

Figure 1. Flow diagram of patient recruitment

Eligibility criteria (inclusion, exclusion criteria)

The inclusion and exclusion criteria are provided in figure 2. Informed consent should be obtained from all patients, and the patients will be asked to notify the researchers if medical changes occurred during the intervention.

Inclusion criteria

 • All female participants who accepted bone densitometry measurement • Women aged 40-55 years with an intact uterus • BMI of < 34.0 kg/m², and > 7 moderate-to-severe hot flushes daily • Women will be considered to be postmenopausal if they had had either > 12 months of spontaneous amenorrhea or > 6 months of spontaneous amenorrhea with serum follicle-stimulating hormone levels of > 40 mIU/mL
Exclusion criteria

 • Diabetes • Secondary obesity • Gastrointestinal diseases • Use of dietary supplements, including calcium, in the three months before enrollment • Pharmacotherapy of lipid disorders or hypertension in the three months before enrollment • Clinically significant acute inflammatory process • Antibiotics intake within the month before enrollment • Participation in a body mass management study • The use of drugs known to modify body mass or food intake • Abuse of alcohol, nicotine, or drugs • Hormone replacement therapy • Vegetarian diet • Use of probiotic enriched or prebiotic enriched products in the three weeks before enrollment • Consumption of products with high dietary fiber content, or consumption of more than 400 g of fermented food a day • Diagnosed osteoporosis

Figure 2. Inclusion and Exclusion criteria

Interventions or exposures

[figure not shown]

Figure 3. Diagram of the intervention period

The intervention period during this study can be seen in figure 3. The diet intervention in this experiment will be performed for 12 weeks, as Ahn et al. (2019) described. Two groups will be designated in this study. Group 1 is the placebo group that will receive a capsule that consists of the excipient. The excipient will be composed of maize starch and maltodextrins (Skrypnik et al., 2019). Group 2 is the probiotic group that will receive a diet capsule consisting of *Lactobacillus acidophilus* with a dose of 1×10^9 CFU with the excipient described by Hosseini et al. (2019). In addition, it is essential to deliver self-administration of probiotic agents orally in the morning with fasting conditions to evaluate probiotic effectiveness. Subsequently, patients will be asked to keep the diet in refrigerated condition (2-7 °C).

Primary endpoints

This study will consider the change from baseline in the frequency and severity of hot flushes as primary endpoints.

Secondary endpoints

Meanwhile, the health-related quality of life, sleep, satisfaction with treatment, and cumulative amenorrhea and breast pain will be considered as secondary endpoints.

Sample size calculation

To calculate sample size, this study refers to the Soleimani et al. (2017) study. Using a formula suggested for clinical trials, having 25 participants in each group will be considered adequate

while considering a type I error (a) of 0.05 and type II error (b) of 0.20 (power $1 - \beta = 80\%$), with 1.61 as the SD and 1.30 as the mean distinction of CTX for markers of bone resorption and BSAP for marker of bone formation as the key variable. By assuming five dropouts in each group, the final sample size will be 30 participants in each group.

Methods assignment of interventions

Randomization will be performed using a computerized random number generator, which generated the random sequence based on simple randomization. All subjects will be identified by a trial identification number and assigned a treatment code. The researchers and participants will be blinded to the treatment code until the end of the study when data will be collected and evaluated. The groups will be decided after the completion of the data analysis.

Variable assessment

All information is containing 3 days dietary records, body composition measurement, and fasting blood samples will be collected at the beginning and end of the study. DIETA 6.0 and 5D computer program by Instytut Żywości i Żywienia, Poland will be used for analyzing 3 days averages of macronutrients and micronutrient intakes. A validated questionnaire obtains personal and demographic information. Anthropometric measurements will be measured using body composition analysis.

Biomarkers of bone turnover and hormones

This study will analyze the biomarkers of bone turnover and hormones as described by Villareal et al. (2016). Briefly, venous blood samples will be obtained after fasting overnight and analyzed in the laboratory. Enzyme-linked immunosorbent assay (ELISA) will be used to measure C-terminal telopeptide of type I collagen (CTX) and tartrate-resistant acid phosphatase isoform-5b (TRAP5b) as markers of bone resorption and bone-specific alkaline phosphatase (BSAP) as a marker of bone formation. Radioimmunoassay will be used to measure N-terminal propeptide of type I procollagen (PINP) as an additional marker of bone formation. ELISA is also used to measure high-molecular-weight adiponectin and insulin-like growth factor-1. Chemiluminescent immunoassays will be used to measure parathyroid hormone (PTH) and cortisol.

Hair sample

A hair strand of 1 cm of length is collected from the occipital region. The sample will be taken by a member of the study team shortly after the hair had been washed with a shampoo not containing functional components. Each woman is instructed on how to wash her hair. Moreover, it will be clearly explained to patients that reliable results could be obtained only by complying with this procedure. Hair spray or hair dye is forbidden during the study (Skrypnik et al., 2019).

Calcium analysis

The calcium contents of the hair and serum will be determined after digestion in 65% (w/w) spectra pure HNO₃ using a Microwave Digestion System. Upon digestion and dilution with deionized water, the concentrations in the mineral solutions are measured using flame atomic absorption spectrometry (Skrypnik et al., 2019).

Bone densitometry analysis

This analysis will be conducted in the accredited laboratory in Poznan, Poland. Subsequently, the subjects are asked to undergo bone mineral densitometry using a DEXA scan. The scan will be performed on a Hologic DXA scan machine.

Products used in the research

1. A capsule consists of Maize starch and maltodextrins for the Placebo Group.
2. A capsule contains *Lactobacillus acidophilus* with a dose of 1×10^9 CFU for the Probiotic Group.

Ascertainment Feasibility

The study will be conducted in the Department of Obesity and Metabolic Disorders Treatment and Clinical Dietetics, Karol Marcinkowski University of Medical Sciences (PUMS), Poznan, Poland. This place receives patients who meet the inclusion criteria described above.

Techniques and actual available equipment

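### The aim (calcium status and bone densitometry), the listed endpoints (hot flushes and symptoms) and the sample-size variable (CTX/BSAP) are three different things, so no listed endpoint answers the aim or carries the stated 80% power

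*Protocol*

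**What the plan says.** - **Title and aim.** The title asks whether the probiotic can "decrease the risk of postmenopausal osteoporosis in women". Under Aim of study, the target is the effect of "supplementation on calcium status and bone densitometry in postmenopausal women".
- **Measurement.** Under Methods & Analysis, "Before and after the intervention, several parameters will be conducted", and the list includes "the bone densitometry analysis in bone using DXA". Under Interventions or exposures, "The diet intervention in this experiment will be performed for 12 weeks". The text describes no later scan.
- **Endpoints.** The primary endpoints are the "change from baseline in the frequency and severity of hot flushes as primary endpoints". The secondary list covers quality of life, sleep and treatment satisfaction, and ends with "cumulative amenorrhea and breast pain will be considered as secondary endpoints". DXA, calcium, CTX and BSAP appear in neither list.
- **Sample size.** The Sample size calculation section takes CTX and BSAP together as the key variable, with a difference of 1.30, an SD of 1.61, type I error 0.05 and power 80%. It arrives at 25 per arm, or 30 after five dropouts per arm. No unit is given. In the reference list, the study cited as its basis is, by its title, a probiotic trial in diabetic hemodialysis patients. The exclusion criteria here begin "Diabetes • Secondary obesity".
- **Densitometry.** The Bone densitometry analysis section gives the laboratory and the scanner make. It gives no skeletal site, precision, expected difference or SD.

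**The concern.** A trial's aim, its endpoints and the variable it is sized on should describe one question. Here each points elsewhere. An analyst who follows the endpoint lists will test hot flushes and symptoms and will report nothing that answers the aim. The 80% power will be quoted for a trial none of whose listed endpoints it was calculated for.

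The bone result is exposed in a second way. DXA is measured and named in the aim, so a 12-week BMD comparison will probably be reported. With no stated power, a non-significant difference could be taken as the answer to the title question when it may only reflect the size of the trial. Calcium status, the other half of the aim, has no listed endpoint and no sizing either.

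**Working it through.** **1. The three statements side by side**

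| Quantity | In the aim? | Listed endpoint? | Sized? |
|---|---|---|---|
| Bone densitometry (DXA) | yes | no | no |
| Calcium status | yes | no | no |
| CTX / BSAP | no | no | yes |
| Hot flush frequency and severity | no | primary | no |
| Quality of life, sleep, satisfaction, amenorrhea, breast pain | no | secondary | no |

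No row has more than one yes.

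**2. Reproducing the protocol's sample size**

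Inputs from the Sample size calculation section: difference 1.30, SD 1.61, alpha 0.05, power 0.80. Sidedness is not stated.

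- Standardised effect: 1.30 / 1.61 = 0.807 SD.
- Two-sided normal formula: n = 2 × [1.61 × (1.960 + 0.842) / 1.30]² = 24.08, rounded up to 25 per arm. A one-sided test gives 19, so the stated figure is the two-sided one.
- Power at 25 per arm: 81% by the normal approximation, 79.9% by the t-test. At 30 per arm the t-test gives 86.8%.
- Dropout: 25 + 5 = 30 per arm, 60 in total.

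The arithmetic is sound for the inputs given. What it does not settle is which marker 1.30/1.61 describes. CTX is a resorption marker and BSAP a formation marker, and one pair without units is given for both.

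**3. What 25 per arm means for 12-week BMD**

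The protocol gives no BMD difference or SD, so the power can only be stated in SD units of the 12-week change (two-sided t-test, alpha 0.05).

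| Assumed true between-arm difference | Power at 25 per arm |
|---|---|
| 0.2 SD | 11% |
| 0.3 SD | 18% |
| 0.5 SD | 41% |
| 0.8 SD | 79% |
| 1.0 SD | 93% |

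- Difference detectable with 80% power: 0.809 SD.
- Half-width of the 95% confidence interval: 2.011 × √(2/25) = 0.569 SD.
- Evaluable women per arm for 80% power (normal formula): 63 at 0.5 SD, 175 at 0.3 SD, 393 at 0.2 SD.

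**4. Can this be turned into percent BMD?**

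Only with outside assumptions. Take the SD of change as √2 × the precision error per scan, with no other variation, and the largest effect as stopping all bone loss for 12/52 = 0.231 year. The range examined is loss of 1–5% per year and precision of 0.5–2%.

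- Least favourable corner (loss 1%, precision 2%): 0.231 / 2.83 = 0.08 SD, power 6%.
- Most favourable corner (loss 5%, precision 0.5%): 1.154 / 0.707 = 1.63 SD, power above 99%.

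The documents give no reason to prefer any part of this range.

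**The case against.** **Trials are commonly sized on one variable, and further unsized measurements are ordinary.** This is right, and a missing BMD power calculation would not be a fault by itself. It matters here because the unsized measurement is a named target of the aim and the sized variable is not an endpoint at all.

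**The sizing is for bone.** This also stands. CTX and BSAP are bone markers, and 25 per arm gives 80% power on the stated inputs. It would be wrong to say that the sizing cannot give any bone answer; it nominally supports one on turnover, though not on BMD.

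**A reader might infer that 12 weeks with 25 per arm is bound to fail for BMD.** The documents do not support that. Under the assumptions in step 4 the power runs from 6% to above 99%, and counting unfavourable combinations only counts cells of a grid that somebody chose. The supportable statement is that the power for BMD is unknown.

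**A reader might infer that the source study makes 1.30/1.61 wrong.** Only its title can be seen here. The title shows a population that this trial excludes, which is a reason to justify the figures. It does not show them to be wrong.

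**Hot flushes may be meant as primary.** The inclusion criteria do require more than seven a day, so the endpoint is not plainly a slip. That makes it more important to decide its rank openly.

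**The analysis plan could settle this.** The protocol itself fixes the aim, the endpoint lists and the sample size, and the conflict lies among those. Figures 1 and 3 are not shown, so a later scan cannot be wholly excluded, but the text describes none.

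**Conclusion.** The point holds as an internal mismatch, and that part needs no outside figure. As written, no listed endpoint answers the aim or the title question, and the stated 80% power attaches to no listed endpoint.

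The 25 per arm is correctly computed for a 0.81 SD difference in a turnover marker, provided 1.30/1.61 can be tied to one marker and unit. For 12-week BMD the power is unknown: 80% requires a true difference of about 0.81 SD of the change, and a difference of 0.5 SD would be found about 41% of the time. These figures assume a two-sided t-test with 25 evaluable women per arm. They do not show that the densitometry aim must fail.

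**What to change.** Make the aim, the endpoint lists and the sample-size variable agree.

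1. List the turnover marker used for sizing as the primary endpoint. Name the one marker and its unit to which 1.30/1.61 refers, and say why values from the cited population apply here.
2. List calcium status and DXA BMD as secondary or exploratory endpoints, and state that calcium status was not sized.
3. Move hot flushes to secondary, or keep them primary and state that the 80% power does not apply to them.
4. Restate the aim, and the title question with it, to match.
5. Keep the DXA scans. Report the between-group difference in 12-week BMD change with a 95% confidence interval, and state that it was not powered and that a non-significant result is not evidence of no effect. Alternatively, give a BMD difference and an SD of change and show the resulting power.

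**Cost.** Scans and duration can stay as planned. The price is a more modest bone claim and either a changed primary endpoint or a restated power. If 1.30/1.61 cannot be tied to a single marker, the sample size must be recalculated and may change.

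### In the text available, harms are detected only through unsolicited, undefined reports, and no endpoint compares adverse events or gastrointestinal tolerability by arm

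*Protocol*

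**What the plan says.** **Detection of harms.** Under Eligibility criteria, next to the sentence on informed consent, the protocol states that "the patients will be asked to notify the researchers if medical changes occurred during the intervention". The readable text does not define adverse events, ask about them, grade them or follow them up.

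**Scheduled assessments.** Variable assessment says that dietary records, body composition and "fasting blood samples will be collected at the beginning and end of the study". The Short Description adds hair calcium and bone densitometry before and after the 12-week intervention. The one questionnaire described covers personal and demographic information.

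**Endpoints.** The primary endpoints are the "change from baseline in the frequency and severity of hot flushes as primary endpoints". The secondary list reads: "the health-related quality of life, sleep, satisfaction with treatment, and cumulative amenorrhea and breast pain will be considered as secondary endpoints".

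**Aim and background.** The stated aim is efficacy: "This study aims to evaluate the effect of *L. acidophilus* supplementation on calcium status and bone densitometry in postmenopausal women". The background says of estrogen and drug therapy that "those treatments increase the risk of cancers and are not prescribed for long-term use". It makes no explicit claim that the probiotic is safer.

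**Supervision.** The section on techniques and equipment places the work under specialist medical control. That is general oversight and does not describe how events are collected.

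**The concern.** Spontaneous notification depends on two steps: the participant must decide that something counts as a medical change, and she must then take the initiative to report it. A new diagnosis or a new prescription would probably pass both steps. Bloating, loose stools or abdominal discomfort may well not. The product is a live bacterium taken by mouth while fasting, and gastrointestinal disease is an exclusion, so the gut is the obvious place to look. No endpoint does so.

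What is at stake is the meaning of a low event count. If the report says that few or no events occurred, a reader cannot tell a well-tolerated capsule from one about which nobody was asked. Blinding makes the reporting threshold likely to be similar in the two arms, but it does not restore events that were never recorded. A statistical analysis plan cannot repair this either: it can tabulate what was collected, not recover symptoms that nobody asked about.

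**Working it through.** **1. The planned size.** The protocol gives SD 1.61, mean difference 1.30, type I error 0.05 and power 80%. Two-sided, n per arm = 2 × [1.61 × (1.960 + 0.842) / 1.30]² = 24.08, which rounds up to 25. Adding five dropouts gives 30. The stated figures reproduce, so no number in the plan is wrong here. The size was set on bone markers, not on harms.

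**2. What complete capture would show.** With zero events in n women, the exact one-sided 95% upper bound on the true rate is 1 − 0.05^(1/n).

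- n = 30: 1 − 0.05^(1/30) = 9.5%
- n = 25 (completers only): 1 − 0.05^(1/25) = 11.3%

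**3. What incomplete capture does.** The documents give neither an event rate p nor a capture fraction c, so both are assumptions and are shown over a range. The chance of at least one report among 30 women is 1 − (1 − p × c)^30.

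| True rate p | c = 100% | c = 75% | c = 50% | c = 25% |
|---|---|---|---|---|
| 1% | 26% | 20% | 14% | 7% |
| 2% | 45% | 36% | 26% | 14% |
| 5% | 79% | 68% | 53% | 31% |
| 10% | 96% | 90% | 79% | 53% |

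With zero reports, the upper bound on the true rate is 9.5% / c: 9.5% at full capture, 12.7% at 75%, 19% at 50% and 38% at 25%. Since c is unknown under spontaneous notification, a reader cannot choose among these bounds.

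**4. What better capture would not do.** Take assumed rates of 5% on placebo and 15% on probiotic, with 30 per arm and a two-sided 0.05 test.

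- Pooled rate 0.10; standard error under no difference = √(0.10 × 0.90 × 2/30) = 0.0775.
- Standard error under the difference = √[(0.05 × 0.95 + 0.15 × 0.85)/30] = 0.0764.
- Power = Φ[(0.10 − 1.960 × 0.0775)/0.0764] = Φ(−0.68) = 25%.

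The same formula for 10% against 30% gives 49%. A comparison of harms at this size is descriptive even when every event is recorded.

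**The case against.** **Participants will be asked about symptoms.** Hot flushes, sleep, quality of life and breast pain are largely self-reported, and the text quoted on timing covers only diet, body composition and blood. It would be wrong to say that nobody asks about symptoms, or that contact is limited to two visits. This stands. Those questions concern menopausal complaints and well-being, however, and would not identify or count an adverse event or a gut symptom.

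**Some endpoints may already reflect tolerability.** Satisfaction with treatment and quality of life are planned in both arms and could be affected by poor tolerability. A reader might infer that breast pain is the only tolerability measure; the secondary list does not support that. These remain indirect scores, and none says what happened to whom.

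**The quoted sentence may not be meant as the whole harms procedure.** It sits beside consent and never calls itself the sole method. Figures 1 and 3 are not shown and consent pages were removed, so contact points or reporting instructions may exist there. This also stands, and it limits the finding to the readable text.

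**Safety is not the aim.** A reader might infer from the background that the trial means to show a safer alternative to estrogen or drugs, and that passive reporting is what defeats this. The documents do not support that reading. The claim is never stated, and the aim is calcium status and bone densitometry. A 12-week placebo-controlled trial with 30 per arm could not address cancer risk or long-term use under any collection method.

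**The rates are assumed.** That is so, and the table above shows the range. The 9.5% bound depends only on the 30 women planned per arm and on zero events with complete capture.

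**Conclusion.** The point holds in a limited form. In the readable protocol, the stated route for detecting harms is unsolicited and undefined, and no endpoint sets adverse events or gastrointestinal tolerability side by side for the two arms. A low count would therefore be hard to interpret, even against placebo.

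The size depends on the unknown capture fraction. Zero reports in 30 women excludes a true rate above 9.5% if capture is complete, and above about 19% if half of events are reported. The choice of gastrointestinal symptoms rests on the nature and route of the product; the documents list no expected events.

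This is an inexpensive improvement to data collection. It does not undermine the efficacy comparison or the sample size. It should be settled before enrolment, because symptoms not asked about at the time cannot be reliably recovered later.

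**What to change.** 1. Keep the notification rule for the period between assessments.
2. Add one short standard checklist of adverse events and gastrointestinal symptoms at the existing baseline and 12-week assessments. Use the same form in both arms and complete it while participants and staff are blinded. The baseline form separates symptoms already present from new ones.
3. Add adverse events and gastrointestinal tolerability by arm as a secondary endpoint, labelled descriptive. Breast pain need not be removed to make room.
4. State that no conclusion will be drawn on safety relative to estrogen or drug treatment, and report zero counts with their upper confidence bound.
5. If Figure 3 or the consent material already contains reporting instructions, refer to them in the main text so that the sources agree.

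**Cost.** One extra form at two assessments that already take place. Asking directly will raise reported event counts in both arms. Recall over 12 weeks may still miss mild events, so capture improves but does not become complete.

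### The daily hot flush entry threshold fits the declared primary endpoints but not the bone and calcium aim, so any bone result would come only from women above that threshold

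*Protocol*

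**What the plan says.** Figure 2 (Inclusion criteria) requires "> 7 moderate-to-severe hot flushes daily", joined to the BMI limit in a single item.

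The Aim of study, in the Short Description, is to evaluate the "effect of *L. acidophilus* supplementation on calcium status and bone densitometry in postmenopausal women". The title asks about the risk of postmenopausal osteoporosis. Neither mentions menopausal symptoms.

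The endpoint sections point elsewhere. Under Primary endpoints the Protocol names the "change from baseline in the frequency and severity of hot flushes as primary endpoints". Under Secondary endpoints it says that "the health-related quality of life, sleep, satisfaction with treatment, and cumulative amenorrhea and breast pain will be considered as secondary endpoints". Neither list contains a bone or calcium variable.

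The Sample size calculation returns to bone: it uses CTX (resorption) and BSAP (formation) as the key variable, with SD 1.61, mean difference 1.30, "type I error (a) of 0.05" and 80% power. The measurement sections cover bone turnover markers and hormones, hair and serum calcium, and DXA.

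On recruitment, Ascertainment Feasibility says only: "This place receives patients who meet the inclusion criteria described above".

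**The concern.** The entry rule and the stated question describe different populations. The question is about bone and calcium after the menopause. The women enrolled must also have more than 7 flushes a day of at least moderate grade, and nothing in the bone and calcium part of the Protocol uses that condition.

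Two things are at stake. First, a bone or calcium result would be reported under a title and aim wider than the women who produced it. Second, correcting the endpoint list alone would not cure this: if a bone variable became primary and Figure 2 stayed as it is, the trial would still exclude every woman with 7 or fewer such flushes a day, by then for no stated reason. Eligibility therefore needs its own line in the correction.

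**Working it through.** **1. Which parts of the Protocol use the threshold**

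| Element | Subject | Does the threshold serve it? |
|---|---|---|
| Title and Aim of study | Osteoporosis risk, calcium status, bone densitometry | No |
| Primary endpoints | Hot flush frequency and severity | Yes: a woman with few flushes at baseline has little room to improve |
| Secondary endpoints | Quality of life, sleep, satisfaction, amenorrhea and breast pain | Compatible with a symptomatic population |
| Sample size calculation | CTX and BSAP | No |
| Bone marker, hair, calcium and DXA sections | Bone and calcium | No |

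The threshold belongs to the symptom part of the Protocol and has no link to the bone part.

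**2. Does the sample size depend on it?**

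Inputs, all from Sample size calculation: difference 1.30, SD 1.61, alpha 0.05 (sidedness not stated), power 0.80.

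- Two-sided normal formula: n per group = 2 × (1.960 + 0.842)² × (1.61/1.30)² = 2 × 7.85 × 1.534 = 24.1, rounded up to 25. This matches the Protocol. Power at 25 per group is 81.5%.
- Two-sided t-test: 25.07 per group, with power 79.9% at 25, so essentially the same.
- A one-sided test gives 19, which does not match, so the plan's figure is two-sided.
- Adding the five assumed dropouts: 25 + 5 = 30 per group, 60 in total, as stated.

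No input refers to hot flushes. On these inputs, deleting the threshold changes neither the sample size nor the power.

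**3. Recruitment**

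The Protocol gives no share of women who meet the threshold and no recruitment rate. If a share f of otherwise eligible women meet it, 60 recruits require 60/f such women. The values of f below are assumptions.

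| Assumed f | Otherwise eligible women needed |
|---|---|
| 50% | 60/0.50 = 120 |
| 20% | 60/0.20 = 300 |
| 10% | 60/0.10 = 600 |
| 5% | 60/0.05 = 1,200 |

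Without the threshold the number is 60. The table shows only how the requirement scales with f. It does not estimate the loss in this trial.

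**The case against.** The strongest reply is that the threshold does have a purpose. Hot flushes are the declared primary endpoints, and a minimum baseline count is a sensible entry rule for them. Deleting it while leaving those endpoints in place would make the Protocol worse, because the primary outcome would then be measured in women not required to have the symptom. On this view the fault is the mismatch between aim and endpoints, and the criterion is only a consequence of it. Most of this stands. A reader might infer that the rule achieves nothing, but the Primary endpoints section contradicts that. The choice between deleting and keeping it cannot be made until the primary endpoint is settled. What survives is that both ways of settling it require a further change, to Figure 2 or to the scope of the bone aim.

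It can also be said that the rule applies to both arms and so does not bias the randomised comparison, that nothing in the Protocol suggests a bone effect that varies with flush frequency, and that other criteria (age 40-55, intact uterus, no vegetarian diet) narrow the population too. This also stands. The harm is to how widely a bone result applies, not to its internal validity.

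A reader might go further and infer that the eligible group is small, that most postmenopausal women are turned away, or that those enrolled are severely symptomatic. The Protocol gives no prevalence, its wording covers moderate as well as severe flushes, and its only feasibility statement, though without numbers, points the other way. A reader might also infer that these women are likelier to start hormone therapy or to withdraw, exhausting the allowance of five losses per group. The Protocol lists hormone replacement therapy as an exclusion but says nothing that links flush frequency to starting it or to withdrawal.

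**Conclusion.** The point holds as a mismatch between the population enrolled and the bone and calcium question. The threshold is mandatory, it fits the declared hot flush endpoints, and it serves neither the aim, nor the CTX/BSAP sizing, nor the bone and calcium measurements. Any bone or calcium finding would rest wholly on women above the threshold. That conclusion follows from the text and needs no outside figure.

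The consequence is limited applicability. The 25 evaluable and 30 randomised per group are unaffected. The recruitment cost is unknown, and the figures from 120 to 1,200 rest entirely on assumed shares of 50% down to 5%.

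**What to change.** Make this change in the same amendment that reconciles the aim with the endpoints.

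- **If bone and calcium are the question:** name a bone or calcium variable as primary (CTX or BSAP, already used for sizing), delete the flush threshold from Figure 2, and record flush count at baseline as a descriptor. The existing 30 per group carries over if the primary variable is the one that the SD of 1.61 and difference of 1.30 describe. A different variable would need its own sizing inputs.
- **If hot flushes stay primary:** keep the threshold and limit the bone and calcium aim and conclusion to women with more than 7 moderate-to-severe flushes a day. The sample size would then need a basis in the flush endpoints, since the present one concerns bone markers.

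The cost of the first route is one line in Figure 2 plus the rewritten endpoint sections. Its downside is that, without the threshold, hot flushes can only be a minor outcome. The second route needs rewording of the aim and planned conclusion plus a new sizing statement, and gives a narrower bone claim. On either route, Ascertainment Feasibility would be stronger with a count of women at the site who meet the final criteria.
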